**Describe the planned research approach including the community engagement approach (13,500 characters):**

**Describe approach**

We will partner with a Federally Qualified Health Center (FQHC) at Valleywise health to identify and recruit patients into the study. Valleywise health is the largest safety-net healthcare organization in Arizona, serving over 430,000 ambulatory visits per year. They serve a patient population that is medically complex with challenging social barriers to healthcare including homelessness, substance abuse, food insecurity, illiteracy, etc. The healthcare team (providers and social workers) are often challenged by limited community resources to assist patient's through SDOH challenges.

We aim to recruit 30 patients (total) into this study to power the results sufficiently. These patients will have an identified SDOH need that is negatively impacting their health (as determined by the FQHC staff). Once referred, the patient will be screened with a SDOH screening tool (the CMS Accountable Health Communities Screening Tool) to establish a

baseline and interviewed to determine their individual needs, they will also complete the Brief Resilience Survey (BRS) in addition to semi-structured qualitative interviews. Screening and interviews will take place by the study coordinator and/or researchers. Once accepted into the study, the study staff will refer the participant to a member of The Open Table to implement The Open Table model (Network Table) and measure specific outcomes over the intervention period. Patient name, phone number, and email will be shared with The Open Table in order for them to contact the participants and learn more about their SDoH needs. The Network Table consists of 10 trained volunteers that will meet bi-weekly to address the patient's SDoH needs, prioritize interventions and meet with the patients as is appropriate and necessary to resolve each identified need. Once the patient's needs have been met, a seat at the table will become available and additional patients will be recruited to the table. If additional needs arise for individual patients (and there is capacity at the table) patients are welcome to rejoin the table to address additional needs throughout the 12-month study period.

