We intend to implement community engagement in 2 ways. First, we will partner with a community organization/501c3 (The Open Table) to bring their model of leveraging social and relationship capital to the healthcare community. Second, we will partner with a Federally Qualified Health Center (FQHC) (Valleywise Health) to help patients with identified SDoH needs that would benefit from enhanced community-based resources. Additionally, we will partner with said FQHC to measure patient-specific impact (outcomes in relation to SDOH) and provider impact (measure impact on burnout).

Patients will be recruited to the study with the assistance of a research coordinator and in partnership with FQHC staff. This study will follow patients and providers (the healthcare team) for up to one-year post-enrollment, or until patient intervention is complete. Baseline data will be collected via structured individual patient interviews and by collecting baseline SDoH data via the CMS Accountable Health Communities Screening Tool, BRS tool. Screening data may be shared with The Open Table so they can better understand the needs of the participant. Once enrolled in the study, patients will be assigned to a Network Table of trained community volunteers that will support patients with a focus on overcoming SDoH needs to improve health. Each "table" of volunteers will be led by a project director, and each volunteer will be trained by The Open Table.

We will also recruit referring providers to the study (anticipate approximately 10 providers). These providers will be asked to complete the Maslach Burnout Index pre/post intervention.

Inclusion criteria: We will include patients that are age 18 or over with an identified SDOH need that impacts healthcare outcomes (identified by the healthcare team).

Exclusion criteria: non-english speaking patients, patients <18 years old, patients who are pregnant.

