Recruitment: Potential participants with SDOH needs that are negatively impacting their healthcare will be referred by the FQHC healthcare team. Patients meeting inclusion criteria will be referred to the research team. Recruiting providers will provide eligible patients with a flyer with the research team contact information, once the flyer is returned to the research team the patient will be contacted for consideration of enrollment and consent. The research team will obtain consent for all patients appropriate for participation in the study. Providers that refer patients to the study will be asked complete a survey of baseline and post-intervention burnout (Maslach burnout inventory).

Measures:

Our primary outcomes will be responses to the following survey questions pre/post intervention: CMS Accountable Health SDOH Screening Tool and the Brief Resilience Scale (BRS).

Secondary outcome measures will include: # of hospitalizations and # of ER visits, # of primary care visits and perceived access to nutritious food, healthcare worker and/or social worker burnout evaluations (pre/post). Additionally, we will complete semi-structured qualitative interviews of each participant pre/post to determine the impact of this intervention on other aspects of their life/health.

Tertiary measures will be provider burnout scores pre and post intervention based on the Maslach Burnout Inventory.

We will obtain baseline data on # of hospitalizations in the prior 12 months, # of ER visits in the prior 12 months, # of primary care visits in the prior 12 months through patient interviews and use of the EMR. Patients will have SDoH screening via the CMS Accountable Health Communities Screening Tool at baseline. Additionally, each enrolled patient will be interviewed at baseline to understand their responses to the primary outcome measurements. To better understand the patient-specific variables that may contribute to SDoH challenges and outcomes we will also collect patient demographics (e.g., age, gender, race, ethnicity, marital status), medical information (e.g., medical comorbidities, current medications), socioeconomic status (e.g., education, income, employment), environmental data (e.g., address, census measures). Provider surveys will be collected using the Maslach Burnout Inventory.(pre and post intervention). These data will be collected via the electronic medical record, survey data from patients, and survey data from medical providers and healthcare staff.

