Post-intervention we will measure patient-specific outcomes including: # of hospitalizations in the prior 12 months, # of ER visits in the prior 12 months, # of primary care visits in the prior 12 months through patient interviews and use of the EMR. Patients will have SDoH screening via the CMS Accountable Health Communities Screening Tool and the Brief Resilience Scale (BRS) after completion of the intervention. We will also collect provider survey's using the Maslach Burnout Inventory.

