#### Statistical Analysis:

Primary outcomes will be measured by:

Difference in proportion (before vs after intervention) in SDOH status and resilience score.

Secondary outcomes will be measured by:

Difference in number of hospitalizations in the 12 months before vs 12 months during intervention, difference in number of ER visits in the 12 months before vs 12 months during intervention, difference in number of primary care visits in the 12 months before vs 12 months during intervention, difference in proportion (before vs after intervention) of patients answering that they perceive they have access to nutritious food, difference in proportion (before vs after intervention) of patients answering that they perceive they have access to nutritious food.

Baseline patient demographics and clinical characteristics will be descriptively summarized. Differences in categorical endpoints before vs after the intervention will be tested using McNemar's test for paired proportions, or exact McNemar's test for small sample sizes. Differences in continuous endpoints before vs after the intervention will be tested using paired t-tests, or appropriate non-parametric test.

The semistructured interview (qualitative data) will be analyzed separately for significant impact, trend and analysis.

Provider data that are recruited for analysis of burnout will be analyzed in difference in proportion to responses pre/post on the Maslach Burnout Inventory. Given the # (10) of participants in this section, we do not expect to reach statistical significance (due to inadequate power) but we will use this as an exploratory outcome.

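### The post-intervention primary measures hang on an undefined completion of the intervention and are not scheduled for patients who stop early, so the before/after SDOH comparison risks overstating benefit

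*Combined protocol and SAP*

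**What the plan says.** - **Trigger for the post measures** (Describe approach, post-intervention paragraph): "Patients will have SDoH screening via the CMS Accountable Health Communities Screening Tool and the Brief Resilience Scale (BRS) after completion of the intervention". No other time point is given for a post CMS screen or BRS.
- **Leaving the table** (Describe approach): "Once the patient's needs have been met, a seat at the table will become available". No other exit is described. Re-entry is allowed: "patients are welcome to rejoin the table to address additional needs throughout the 12-month study period".
- **Length of follow-up** (Describe approach): patients are followed "for up to one-year post-enrollment, or until patient intervention is complete". No primary assessment is attached to the one-year limit.
- **Primary analysis** (Statistical Analysis): "Difference in proportion (before vs after intervention) in SDOH status and resilience score". Categorical endpoints "will be tested using McNemar's test for paired proportions" or its exact version, and continuous endpoints by paired t-test or a non-parametric alternative.
- **Power** (Power Analysis): worked with 30 patients, with no allowance for loss.

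The document states no analysis population, no missing-data or withdrawal rule, and no instruction to assess patients who stop early. It does not say that they are excluded either.

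**The concern.** The question is who gets a post value at all. Someone who enrols but is never reached by the table, stops attending, or leaves with needs open has not obviously completed anything, so staff following the text would have no prompt to repeat the CMS screen or BRS. Both primary tests need a before and an after value, and such a patient drops out of both.

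For SDOH status this loss is unlikely to be neutral, because unmet need is both a likely reason for having no post value and the thing being measured. There is no comparison group in which the distortion would show. The approach section describes a clinic population that includes people facing homelessness and substance abuse, so loss of contact is foreseeable. Aim 2 could end up answered mainly for patients in whom the table worked, and Describe Outcomes intends the data as proof of concept for extending the model to other populations.

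**Working it through.** **The plan's own figure.** The Power Analysis claims at least 80% power with 30 patients at alpha 0.05. The before/after proportions behind it are not in the text (a table may have been lost), so it cannot be reproduced and is not called wrong here. It treats 30 recruited patients as 30 complete pairs.

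**Inputs.** From the plan: 30 patients, paired tests, alpha 0.05 (sidedness not stated; two-sided assumed). Assumed, because the plan gives nothing: the chances of improving and worsening, and the chance of having no post value in each group.

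**Check 1: no true net change, outcome-dependent loss.** Let a proportion p improve and the same proportion p worsen. Let the loss rates be L_i (improved), L_u (unchanged) and L_w (worsened). Then:

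- observed improved: a = p(1 − L_i)
- observed worsened: b = p(1 − L_w)
- fraction measured: K = a + b + (1 − 2p)(1 − L_u)
- pairs = 30K; apparent net improvement = (a − b)/K

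The favourable false-positive rate sums the trinomial probabilities (30 patients; a, b, 1 − a − b) over outcomes with more improved than worsened and McNemar p ≤ 0.05.

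Worked case, p = 0.25 and loss 10/30/50%: a = 0.225, b = 0.125, K = 0.225 + 0.125 + 0.50 × 0.70 = 0.70. Pairs = 21; apparent net = 0.10/0.70 = 14.3 points.

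| p each way | Loss improved/unchanged/worsened | Pairs | Spurious net | False positive, exact | False positive, asymptotic |
|---|---|---|---|---|---|
| 15% | none | 30 | 0 | 1.0% | 2.2% |
| 25% | none | 30 | 0 | 1.4% | 2.4% |
| 35% | none | 30 | 0 | 1.5% | 2.7% |
| 15% | 10/30/30% | 21.9 | 4.1 | 2.0% | 4.6% |
| 15% | 10/20/40% | 23.6 | 5.7 | 2.8% | 6.6% |
| 25% | 10/30/30% | 22.5 | 6.7 | 3.4% | 5.5% |
| 25% | 10/30/50% | 21.0 | 14.3 | 8.5% | 13.1% |
| 35% | 5/30/60% | 20.5 | 28.2 | 24.8% | 32.6% |

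The false-positive rate is driven by losing worsened patients more often than improved ones. Losing unchanged patients leaves McNemar's p-value alone (they are concordant pairs) but shrinks the denominator and so enlarges the apparent change.

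**Check 2: a different loss model.** Let a fraction s of all patients stop, all drawn proportionally from non-improvers, with p = 0.20. Apparent net = [p − p(1 − s/(1 − p))]/(1 − s). At s = 30%: (0.20 − 0.20 × 0.625)/0.70 = 10.7 points. For s = 10, 20, 30 and 40% the net is 2.8, 6.2, 10.7 and 16.7 points, and the exact false-positive rate is 2.0, 3.4, 5.6 and 9.2%, against 1.2% with no loss.

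**Check 3: a real effect.** Suppose 12 of 30 (40%) truly resolve a need and every stopper is unresolved and unmeasured. The reported rate becomes 12/27 = 44%, 12/24 = 50%, 12/21 = 57% or 12/18 = 67% at 10, 20, 30 or 40% stopping. Dividing by all 30 restores 40%.

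**BRS.** No calculation was made. Resilience is not defined by needs being met, so the change in unmeasured patients could go either way.

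**The case against.** A reader might infer that completion means needs met, so that every unresolved patient is shut out of the primary analysis. The documents do not support that. A freed seat is not called completion. The study period is described as 12 months, follow-up runs to one year, and the secondary analysis compares the 12 months before with 12 months during intervention. A patient still at the table with open needs at one year could reasonably be screened then. The Measures text also plans post-intervention interviews for every participant, which counts against a plan that contacts only resolved patients.

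A reader might also infer that bias in both primary outcomes is established. It is not. The exclusion is read from silence, every loss rate above is assumed, and the calculation covers a binary endpoint only.

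The null scenario has its own weakness. Eligibility requires an identified need, so an any-need status starts near 100% and few patients can worsen (domain-level status may differ). With less selective loss the inflation is modest: 3.4% rather than 8.5% in the 25% case when unchanged and worsened patients are lost equally.

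All of this limits the claim without removing it. Neither the one-year limit nor the interview plan schedules the CMS tool or BRS for someone who stopped, and where few can worsen, the distortion moves from the p-value to the reported resolution rate (check 3).

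**Conclusion.** The concern holds as a gap that carries a risk of unknown size. Completion is undefined, no primary assessment is scheduled for patients who are never reached or who stop early, and the tests drop anyone without a post value. For SDOH status the probable direction is toward benefit; for the BRS it is only plausible.

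Under the loss patterns in check 1, the spurious net improvement is about 4 to 28 points and the favourable false-positive rate about 2 to 25% (exact), against 1 to 1.5% with all 30 measured. Check 2 gives a slightly smaller distortion at its mildest, 2.8 points with 10% stopping. These figures rest on loss that depends on outcome. If few patients stop, or those who stop are screened anyway, the problem largely disappears. The plan should be changed, because post values not collected on time cannot be recovered later.

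**What to change.** 1. **Describe approach, post-intervention paragraph.** Replace the trigger with wording such as: the post CMS screen and BRS will be obtained from every enrolled patient at a stated time (for example 12 months after enrolment), by phone if needed, whether or not the patient started, stopped or completed the Open Table, unless consent to follow-up is withdrawn. Reconcile the follow-up sentence with this, so that follow-up does not end for the primary measures when the intervention does.
2. **Statistical Analysis.** Name all enrolled patients as the primary analysis set. Report how many lack a post value and why. Add a simple sensitivity analysis for missing post SDOH status, such as counting it as unresolved. For a patient with the need at baseline this adds a concordant pair: it corrects the denominator but leaves McNemar's p-value unchanged, so collecting the data is the main remedy. Label any completers-only result as supportive.

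Cost: wording in two places and a few extra phone contacts by the existing coordinator. The sample size and tests stay as they are. The reported change will probably be smaller than a completers-only figure.

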#### Power Analysis:

With a sample size of 30, both combinations of before/after proportions are expected to have at least 80% power, assuming we use alpha 0.05 for testing. If we correct for multiple testing (2 primary outcomes) using a Bonferroni-adjusted alpha of 0.025, both combinations of proportion assumptions are expected to have close to or above 80% power to detect a difference before vs after intervention.

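### The post-intervention SDOH screen and resilience scale have no fixed date, and the follow-up, measurement and analysis text disagree on the post-enrolment utilisation window

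*Combined protocol and SAP*

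**What the plan says.** The SDOH screening tool and the Brief Resilience Scale (BRS) are the primary outcomes, compared before and after the intervention. Under Describe approach, the post-intervention text has patients screened with the SDOH tool "and the Brief Resilience Scale (BRS) after completion of the intervention". No month, visit or window is given, and Statistical Analysis names no time point for the primary contrast.

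Three statements under Describe approach bear on when completion might fall:

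- When a patient's needs have been met, "a seat at the table will become available and additional patients will be recruited to the table".
- If there is capacity, "patients are welcome to rejoin the table to address additional needs throughout the 12-month study period".
- Patients and providers are followed "for up to one-year post-enrollment, or until patient intervention is complete".

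For utilisation, the baseline text reads "We will obtain baseline data on # of hospitalizations in the prior 12 months". The post-intervention text reads "Post-intervention we will measure patient-specific outcomes including: # of hospitalizations in the prior 12 months". Both go on to treat ER and primary care visits in the same way, using patient interviews and the electronic record. Statistical Analysis describes the contrast as "Difference in number of hospitalizations in the 12 months before vs 12 months during intervention", and likewise for the other two counts.

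**The concern.** Two separate problems follow from the missing date.

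First, the nearest thing to completion in the text is the point at which needs are met, and that is itself an outcome. If the post screen follows it, resolved patients are read soon after success, before any need can return, while the others are read later, up to one year. A primary outcome would then partly reflect when it was measured.

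Second, the two descriptions of the post-enrolment count agree only if every patient is assessed at month 12. The follow-up rule does not ensure this. For an early finisher, the look-back described under the post-intervention measures reaches into the year already counted at baseline. The period named in Statistical Analysis cannot be filled if follow-up has ended. All three utilisation outcomes are exposed, and staff following different sentences could collect different data.

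**Working it through.** The plan gives no figure for assessment timing to reproduce. Its power statement (at least 80% with 30 patients) lists no before/after proportions and does not bear on this point.

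**Utilisation window.** Inputs from the plan: a 12-month count before baseline, a 12-month look-back at the post assessment, and follow-up that may end before one year. Assumptions: the intervention starts at enrolment (month 0), the post assessment is at month m, and the event rate is constant at λ per month before enrolment and RR × λ after it.

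- Baseline count: 12λ.
- Post count on the look-back reading: (12 − m)λ + m × RR × λ.
- Observed ratio: (12 − m + m × RR)/12, so observed fall = (m/12) × (1 − RR).
- Counting only on-study months against 12 baseline months, with no effect (RR = 1): ratio m/12, an apparent fall of 1 − m/12.

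| Month of post assessment | Baseline-year months in look-back | Observed fall, true fall 50% | Apparent fall, on-study months only, no effect |
|---|---|---|---|
| 3 | 9 | 3/12 × 50% = 12.5% | 75% |
| 6 | 6 | 6/12 × 50% = 25% | 50% |
| 9 | 3 | 9/12 × 50% = 37.5% | 25% |
| 12 | 0 | 50% | 0% |

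So the error can run either way, depending on which sentence is followed. It vanishes only at month 12. The same arithmetic applies to primary care visits: a true rise would be diluted on the first reading and could look like a fall on the second.

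**Timing of the SDOH reading (illustration only).** No input here comes from the plan. Assume that all patients are in need at baseline, the table has no effect, a met need gives a negative screen, needs resolve with monthly probability r and recur with monthly probability q, and nobody rejoins.

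- Need-free at a fixed month 12: [r/(r + q)] × [1 − (1 − r − q)^12].
- Need-free if read at first resolution, or at month 12 if never resolved: 1 − (1 − r)^12.

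With r = 5%, the second is 1 − 0.95^12 = 46.0%. The gap over the fixed reading depends on q:

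- q = 0: no gap.
- q = 2%: 4.4 points.
- q = 5%: 10.1 points.
- q = 10%: fixed value (0.05/0.15) × (1 − 0.85^12) = 28.6%, gap 17.4 points, or about 5 of 30 patients (30 × 0.174 = 5.2).

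With r = 3% and q = 5%, the values are 23.7% and 30.6%, a gap of 6.9 points. The direction is clear if needs recur; the size cannot be known from the plan. No such calculation applies to the BRS, which decides neither entry nor release of a seat.

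**The case against.** The strongest reply is that the plan points to a twelve-month assessment. It caps follow-up at one year, speaks of a twelve-month study period, and has an analysis section that compares twelve months before with twelve months during. It never calls a met need completion, and the option to rejoin suggests that the intervention continues. Assessment at the end of an intervention is also a legitimate choice in a preliminary study with a feasibility aim. Much of this stands: a one-year limit exists and the twelve-month reading is reasonable. But the follow-up sentence offers an earlier end as an alternative, and nothing says which reading governs.

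A reader might go further and infer that patients are screened as soon as their needs are met, or that unresolved patients are never screened. The documents state neither, and the one-year cap argues against the second.

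A reader might also take false rejection of the primary test as the measure of harm. That is not a fair measure of the timing problem. With 30 patients and one-way changes, exact two-sided McNemar at 0.05 rejects from 6 changes (2 × 0.5^6 = 0.031). In the no-effect illustration, a fixed month-12 visit already rejects in 90% of trials at 5%/10% and 75% at 3%/5%, against 99.9% and 93% when read at first resolution. Most of that rejection comes from following a cohort selected for need without a control group, which a fixed visit does not cure. The illustration also leaves out rejoining, which could delay the reading for some patients, so its gaps are upper values for the assumed rates.

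Finally, utilisation is secondary and drawn partly from the electronic record, so the window might be re-cut at analysis for recorded events. That helps only in part, because interviews are the other source.

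**Conclusion.** The point holds in a limited form. The post SDOH screen and BRS have an outer limit but no fixed date, and completion is undefined. The text therefore leaves room for an outcome-dependent SDOH reading without prescribing one. Any resulting bias favours improvement, requires needs to recur, and is of unknown size; the BRS is affected only because follow-up length varies.

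The utilisation conflict is firmer. For anyone finishing before month 12, the follow-up, measurement and analysis statements cannot all be met. A true 50% fall would be read as 12.5% to 37.5% for finishes between months 3 and 9, or a 50% fall would appear from nothing at month 6 if only on-study months are counted. These figures assume constant event rates before and after enrolment and an effect that starts at enrolment. How many patients would finish early is not stated. The documents do not support a claim that utilisation is always biased towards no change.

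**What to change.** Make the primary post SDOH screen and BRS a single assessment at 12 months from each patient's own enrolment, within a stated window (for example plus or minus 1 month), for every enrolled patient regardless of table status or rejoining. Count hospitalisations, ER visits and primary care visits in the 12 months from enrolment against the 12 months before it. Amend the follow-up sentence, the post-intervention measures and Statistical Analysis to agree. Define completion, and keep any screen taken at completion as descriptive. This changes when outcomes are measured, not the support that patients receive.

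The cost is real. Early finishers must be retained or re-contacted to month 12 in a population that includes homelessness, with some risk of dropout at n = 30. The observed SDOH improvement may be smaller. Patients enrolled late, as seats open, need follow-up to their own month 12, which lengthens the study if the twelve-month period was meant study-wide. The change should be made before early finishers leave follow-up, because a missed month-12 screen may not be recoverable.
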